### 12.2.3. Definition of Adverse Events of Special Interest (AESI)

An AESI is an AE/SAE of scientific and/or medical concern, specific to the product or program for which ongoing monitoring and rapid communication by the Investigator to the sponsor is required. Such AEs normally require thorough documentation and investigation in order to characterize them.

The following events are considered AESIs in this study:

- reintubation events
- delirium
- unplanned sedation/somnolence
- altered mental status
- sudden loss of consciousness

Such events should be reported on the AESI form to Sage or designee within 72 hours. If the AESI also qualifies as an SAE, an SAE form should be submitted per the guidelines per Section 12.2.6.

The investigator should provide additional details on the AESI form for the following AESIs as specified below:

- for reintubation events, include the reason for reintubation
- for delirium, document whether the participant had regained an appropriate state of orientation at some point after being extubated prior to onset of delirium

**12.2.4. Relationship to Investigational Product**

The investigator must make the determination of relationship to the IP for each AE (not related, related). The following definitions should be considered when evaluating the relationship of AEs, SAEs, and AESIs to the IP.

Not Related	An AE will be considered “not related” to the use of the IP if there is not a reasonable possibility that the event has been caused by the IP. Factors pointing towards this assessment include but are not limited to: the lack of temporal relationship between administration of the IP and the event, the presence of biologically implausible relationship between the product and the AE, or the presence of a more likely alternative explanation for the AE
Related	An AE will be considered “related” to the use of the IP if there is a reasonable possibility that the event may have been caused by the product under investigation. Factors that point towards this assessment include but are not limited to: a positive rechallenge, a reasonable temporal sequence between administration of the drug and the event, a known response pattern of the suspected drug, improvement following discontinuation or dose reduction, a biologically plausible relationship between the drug and the AE, or a lack of alternative explanation for the AE

For AESIs deemed “not related” to IP, the suspected cause of the event should be recorded on the AESI form.

**12.2.5. Recording Adverse Events**

Adverse events spontaneously reported by the participant and/or in response to an open question from the study personnel or observed will be recorded during the study at the investigational site. The AE term should be reported in standard medical terminology when possible. For each AE, the investigator will evaluate and report the onset and resolution (date and time), intensity, causality, seriousness criterion(ia), action taken, and outcome (if applicable), and whether the AE resulted in IP dose reduction, discontinuation of the IP or withdrawal from the study.

Intensity will be assessed according to the guidelines for the National Cancer Institute Common Terminology Criteria for Adverse Events (CTCAE) Version 5.0. The CTCAE provides a grading (severity) scale for AEs, with unique clinical descriptions of severity based on the general guidance listed below:

**Table 2: Common Terminology Criteria for Adverse Events**

Grade	Criteria
1	Mild; asymptomatic or mild symptoms; clinical or diagnostic observations only; intervention not indicated
2	Moderate; minimal, local, or noninvasive intervention such as packing or cautery indicated, limiting age-appropriate instrumental activities of daily living (ADL)
3	Severe; or medically significant but not immediately life-threatening; hospitalization or prolongation of hospitalization indicated; disabling; limiting self-care ADL

Grade	Criteria
4	Life-threatening consequences; urgent indications indicated
5	Death related to adverse event

It is important to distinguish between seriousness and severity. Severity is a measure of intensity whereas seriousness is defined by the criteria under Section 12.2.2. An AE of severe intensity may not necessarily be considered serious.

#### 12.2.6. Reporting Serious Adverse Events

Except as specified below, in order to adhere to all applicable laws and regulations for reporting an SAE(s), the study site must notify Sage or designee within 24 hours of the study site staff becoming aware of the SAE(s). The investigator must complete, sign and date the SAE reporting form, verify the accuracy of the information recorded on the SAE reporting form with the corresponding source documents, and send a copy to Sage or designee.

Additional follow-up information, if required or available, should all be sent to Sage or designee within 24 hours of receipt on a follow-up SAE reporting form and placed with the original SAE information and kept with the appropriate section of the CRF and/or study file.

SAEs occurring after the designated follow-up time for the study, should be reported to Sage or designee according to the timelines noted above only if the investigator considers the SAE related to IP.

Sage, or designee, is responsible for notifying the relevant regulatory authorities of certain events. It is the principal investigator's responsibility to notify the IRB/IEC of all SAEs that occur at his or her site. Investigators will also be notified of all suspected unexpected serious adverse reactions (SUSARs) that occur during the clinical study. IRBs/IECs will be notified of SAEs and/or SUSARs as required by local law.

#### **Exceptions to the Standard SAE Reporting Requirements**

Unless otherwise noted below, if the event is included in Table 3, an SAE reporting form does not need to be completed, but the event should be recorded on the CRF. The following exceptions apply:

- Please Note: If the event is on the list and if the event was considered by the investigator to be related to IP then the SAE reporting form will be completed, and the SAE will be reported to Sage per standard SAE reporting requirements. The SAE form for such an event has to be sent to Sage or designee within 24 hours of the site becoming aware of the SAE.
- Please Note: If the event is on the list, but the outcome is fatal, the mortality CRF will be completed, the SAE reporting form will be completed, and the SAE will be reported to Sage per standard SAE reporting requirements. The SAE form for such an event has to be sent to Sage or designee within 24 hours of the site becoming aware of the SAE. The mortality CRF will capture the actual cause of death as well as the category of the cause of death.

**Table 3: List of Common ICU Comorbidities**

Complications of Mechanical Ventilatory Support	Infectious Complications
Pulmonary barotrauma / pneumothorax	Skin and soft tissue infection
Ventilator associated pneumonia	Sepsis or bacteremia
Cardiac and Vascular Events	Septic shock
Tachyarrhythmias such as:	Pneumonia
Atrial fibrillation	Urinary tract infection or urosepsis
Ventricular tachycardia	Catheter site infections
Ventricular fibrillation	Gastrointestinal
Pulmonary embolism	Esophageal, gastric or duodenal ulcer
Thromboembolic event (other than pulmonary)	Gastrointestinal bleeding
Myocardial infarction	Other
Stroke / cerebrovascular accident	Acute renal failure
Hypotension	Complications of procedures

### 12.3. Pregnancy

If a participant becomes pregnant after initiating IP, pregnancy information must be collected and recorded on the pregnancy form and submitted to the sponsor within 24 hours of learning of the pregnancy. Details will be collected for all pregnancies for which conception was likely to have occurred after the start of IP administration until 5 terminal half-lives following the last administration of IP or until the completion of the study whichever is longer. Any pregnancy occurring in that time frame will be followed until delivery or termination of the pregnancy.

The participant will be followed to determine the outcome of the pregnancy. The outcome of all pregnancies (eg, spontaneous abortion, elective abortion, normal birth) must be followed and documented even if the participant was discontinued from the study. The investigator will collect follow-up information on the participant and the neonate, and the information will be forwarded to Sage or designee. Generally, follow-up will not be required for longer than 6 to 8 weeks beyond the estimated delivery date. Any termination of pregnancy will be reported, regardless of fetal status (presence or absence of anomalies) or indication for the procedure.

Pregnancy in itself is not regarded as an AE unless there is a suspicion that an IP may have interfered with the effectiveness of a contraceptive medication. Any complication during pregnancy (eg, anemia, infections, pre-eclampsia) should be reported as an AE/SAE. If the outcome of the pregnancy meets the criteria for immediate classification as an SAE (ie, spontaneous abortion, stillbirth, neonatal death), the Investigator should follow the procedures for reporting an SAE.

## **12.4. Overdose**

An overdose will be considered to have occurred if the infusion rate exceeds the recommended rate by 10% at any point during the infusion and/or the total dose administered exceeds 10% of the protocol-defined total dose. Overdoses are not considered AEs and should not be recorded as an AE on the CRF; however, all overdoses must be recorded on an Overdose form and sent to Sage or designee within 24 hours of the site becoming aware of the overdose. An overdose must be reported to Sage or designee even if the overdose does not result in an AE.

## 13. STATISTICS

Detailed description of the interim and final analyses to be performed in the study will be provided in the statistical analysis plan (SAP). To avoid a potentially biased estimate of the event rate in each arm at the time of the interim analysis, both the interim analyses and final analysis will incorporate all available data from all participants in the study in the analysis population, regardless of whether participants have reached Day 28. The SAP will be finalized and approved prior to database lock of the interim analysis. Any changes/additions to the SAP following database lock will be described in detail in the clinical study report.

### 13.1. Data Analysis Sets

The Randomized Set is defined as all randomized participants (based on treatment as randomized).

The Full Analysis Set is defined as all randomized participants who initiated IV infusion of brexanolone or placebo (based on treatment as randomized).

Per Protocol (PP) Set is defined as all randomized participants (based on treatment as randomized) with no major protocol deviations. This is a subset of the Randomized Set.

The Safety Set will include all participants who initiated IV infusion of brexanolone or placebo (based on actual treatment received).

### 13.2. Handling of Missing Data

Every attempt will be made to avoid missing data. All participants, including those with missing data, will be used in the analyses, as per the analysis sets defined in Section 13.1. The primary analysis method will use all nonmissing data available. In addition, tipping-point analyses will be conducted as sensitivity analyses to assess the impact of missing data.

### 13.3. General Considerations

All participant data, including those that are derived, that support the tables and figures will be presented in the participant data listings. Some data may be presented only in participant data listing, some may be presented with a corresponding table or figure; these will be indicated in relevant sections below. Unless otherwise specified in the SAP, baseline is defined as the last measurement prior to the start of IP infusion.

Continuous endpoints will be summarized with number (n), mean, standard deviation, median, minimum, and maximum. In addition, change from baseline values will be calculated at each time point and summarized descriptively. For categorical endpoints, descriptive summaries will include counts and percentages.

### 13.4. Demographics and Baseline Characteristics

Demographic data, such as age, race, and ethnicity, and baseline characteristics, such as height and weight will be summarized using the Safety Set.

Medical history will be listed by participant.

### 13.5. Efficacy Analysis

The primary endpoint of proportion of participants alive and free of respiratory failure at Day 28 will be summarized using a logistic regression, adjusting for age group. The odds ratio and difference in proportions will be estimated. The secondary endpoint of all-cause mortality through Day 28 will be analyzed using both the Kaplan-Meier method for time to death and the logistic regression model for the proportion of deaths. [REDACTED]

[REDACTED] All efficacy summaries will be performed on the Full Analysis Set. In addition, if over 5% of randomized participants do not receive IP, a sensitivity analysis of the primary endpoint will be conducted on the Randomized Set.

### 13.6. Safety Analyses

Safety and tolerability of brexanolone will be evaluated by the incidence of treatment-emergent AEs, changes from baseline in vital signs, [REDACTED], clinical laboratory evaluations, and 12-lead ECG. Safety data will be listed by participant and summarized by treatment. All safety summaries will be performed on the Safety Set.

#### 13.6.1. Adverse Events

AEs will be coded using Medical Dictionary for Regulatory Activities (MedDRA) Version 23.0 or higher. A treatment-emergent adverse event (TEAE) is defined as an AE with onset after the start of IP. The analysis of AEs will be based on the concept of TEAEs. The incidence of TEAEs will be summarized by System Organ Class and preferred term. In addition, summaries will be provided for TEAEs Grade 3 and above per CTCAE guidelines and by causality (related, not related) to IP.

Any TEAEs leading to IP discontinuation, dose reduction, or study withdrawal and any treatment-emergent SAEs and AESIs will be summarized.

All AEs, SAEs, and AESIs (including those with onset or worsening before the start of IP) through the end of the study will be listed.

#### 13.6.2. Clinical Laboratory Evaluations

Laboratory parameters in [Table 4](#) will be summarized in standard units and mean changes from baseline will be presented.

**Table 4: Summary of Clinical Laboratory Analytes**

Biochemistry	Renal Panel: glucose, calcium, phosphorus, blood urea nitrogen, creatinine, sodium, potassium, chloride, bicarbonate Hepatic Panel: albumin, alanine aminotransferase, aspartate aminotransferase, total bilirubin, direct bilirubin, indirect bilirubin, alkaline phosphatase, total protein, lactate dehydrogenase, gamma glutamyl transferase, c-reactive protein
Hematology	red blood cell count, hemoglobin, hematocrit, white blood cell count with differential, platelet count, erythrocyte sedimentation rate
Coagulation	Activated partial thromboplastin time and prothrombin time

Normal ranges for each parameter in Table 4 will be provided by the laboratory; shift from baseline to postbaseline values and abnormality of results will be provided. Potentially clinically significant values will be summarized by treatment. Clinical laboratory results will be listed by participant and timing of collection.

### 13.6.3. Vital Signs

Vital sign results at each visit and mean changes from baseline will be summarized by scheduled visit. Potentially clinically significant values will be summarized by treatment. Vital sign results will be listed by participant and timing of collection.

### 13.6.4. 12-Lead Electrocardiogram

Mean ECG data will be summarized by visit. Electrocardiogram findings will be listed by participant and timing of collection.

[REDACTED]

### 13.6.6. Prior and Concomitant Medications

Medications will be recorded at each study visit during the study and may be coded using World Health Organization-Drug dictionary Global B3 March 2020, or later.

Medications taken prior to the initiation of the start of IP will be denoted “Prior”. Those medications taken prior to the initiation of the IP and continuing beyond the initiation of the IP or those medications started at the same time or after the initiation of the IP will be denoted “Concomitant”.

Medications will be presented according to whether they are “Prior” or “Concomitant” as defined above. If medication dates are incomplete and it is not clear whether the medication was concomitant, it will be assumed to be concomitant.

Data summarized for the following classes of medications will include the dose, duration, total dose over the hospitalized study period, and indication for use:

- CNS depressants (eg, benzodiazepines, opioids/opiates, barbiturates, propofol)

- other agents utilized for sedation effects (eg, dexmedetomidine)
- drugs administered to treat or prevent ICU delirium (eg, antipsychotics, atypical antipsychotics, or other agents intended for delirium treatment)

## 13.8. Sample Size and Power

The sample size of approximately 100 participants would provide 80% power to detect a treatment difference of 27% in proportions of the primary endpoint of participants being alive and free of respiratory failure at Day 28, assuming the proportion is 50% for the placebo group and 77% for the brexanolone group.

### 13.8.1. Interim and Data Monitoring Committee Analyses

#### 13.8.1.1. Interim Analysis

An interim analysis is planned when about 50% of the total planned number of participants have completed Day 28. This will include summary statistics on the primary endpoint, conducted by a statistical group independent of Sage. The interim data, including safety data will be reviewed by the DMC to evaluate the possibility of stopping the study for futility or safety. Since the sponsor will be kept uninformed of the response rates at the time of the interim analysis, no statistical adjustment will be made to the level of significance for hypothesis testing at the end of the study.

Upon review of data collected at Day 28 for 25 participants in each arm (50 participants total), the statistical rules are:

- **to stop the study for safety** if the difference in the observed mortality rate is more than 4% greater in the brexanolone arm compared to placebo.
- **to stop the study for futility** if the observed difference in the response rates of the primary endpoint (brexanolone response rate – control response rate) is less than 4%.

The aim of the stopping rule for safety is to ensure that there is a reasonably high probability of stopping the study when there is a true underlying excess risk of mortality with the use of IP, and a reasonably low probability of stopping the study when there is no such risk.

The aim of the stopping rule for futility is to ensure that there is a reasonably high probability of stopping the study when IP is ineffective, and a reasonably low probability of stopping the study when IP is efficacious.

To avoid potentially biased estimates of the event rate in each arm at the time of the interim analysis, all available data for the selected variables will be incorporated from all participants in the analysis population, regardless of whether participants have reached Day 28.

A detailed description of the interim analysis is included in the SAP.

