## 5. INTRODUCTION

Multiple approaches should be sought to mitigate the clinical and public health impact of COVID-19. While several approaches are being investigated with an aim to lower viral load and develop vaccines, an approach to improving respiratory function in COVID-19 patients with respiratory failure is urgently needed. Brexanolone (Zulresso™) is an FDA-approved intravenous (IV) infusion for the treatment of postpartum depression (PPD) in adults. Extensive safety experience in Intensive Care Unit (ICU) was gained during development of a separate indication for super-refractory status epilepticus (SRSE). Based on its unique pharmacology targeting multiple subtypes of GABAA receptors, brexanolone has the potential to attenuate the impact of COVID-19 in ventilated patients through multiple mechanisms of action. Preclinical evidence to date suggests that brexanolone is likely to have the following beneficial effects in the clinic: anti-inflammatory and fluid clearance effects via direct action on GABAA receptors located in human alveolar epithelial cells; anti-inflammatory and antiviral effects via inhibition of toll-like receptors and reduction in proinflammatory cytokines; and direct effects on pulmonary function through direct effects on smooth muscle in the lung, reducing shunting and improving partial pressure of arterial oxygen (PaO2).

Severe forms of infection with SARS-CoV-2 produce significant impairment of respiratory function, including acute lung inflammation and acute respiratory distress syndrome (ARDS) (Wujtewicz 2020). Although epidemiological data are rapidly evolving, preliminary reports show that pulmonary impact severe enough to warrant critical care treatment is occurring in 3 to 6% of infected patients (CDC COVID-19 Response Team 2020; Wujtewicz 2020). Data from United Kingdom and from Seattle both suggest that of patients with COVID-19 in critical care, >75% require mechanical ventilation and up to approximately 50% do not survive (Bhatraju 2020; ICNARC 2020). The respiratory symptoms associated with morbidity are driven by factors including vasoconstriction, pulmonary edema, and inflammation secondary to cytokine activation. In addition to viral-induced respiratory trauma, ventilator support that is provided to address ARDS can also exacerbate lung damage and lead to a negative spiral that further contributes to morbidity and mortality.

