### 7.4.1. Data Monitoring Committee

The DMC will review available unblinded safety data regularly (at least every month). The DMC will also have access to unblinded efficacy data as necessary. Refer to Section 13.8.1.2 for additional details. The DMC will be comprised of experienced members and will apply medical and statistical judgment during the performance of their activities according to a DMC charter.

The DMC will be provided with all SAEs (including fatalities) and AESIs on an ongoing basis.

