### 7.4.2. Safety Criteria for Adjustment or Stopping Doses

Enrollment in the study will be discontinued if the DMC determines that any of the following criteria have been met:

1. there is an increased risk of mortality due to brexanolone
2. there is an increased risk of ICU delirium due to brexanolone
3. there is an increased risk of prolonged intubation due to brexanolone
4. there is an increased risk of reintubation due to brexanolone

After each data review, the DMC may recommend that the study continue without modifications, continue with modifications, or be terminated, or that study treatment or enrollment is suspended. The DMC may also recommend stopping the study for futility at the time of interim analysis.

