## 5.2. Sample Size and Power

The sample size of approximately 100 participants would provide 80% power to detect a treatment difference of 27% in proportion of participants alive and free of respiratory failure at Day 28. The sample size is computed assuming proportion of 50% for the placebo group and 77% for the brexanolone group using Chi-square test with a two-sided Type I error rate (alpha) of 0.05.

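### Does the interim mortality rule's unstated false-stop rate, about 30-34% if applied literally, call for a change to the plan or to the 80% power claim?

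*Protocol*

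**What the plan says.** Protocol 13.8.1.1 sets two rules for the interim look at 25 participants per arm. The safety rule stops the study "if the difference in the observed mortality rate is more than 4% greater in the brexanolone arm compared to placebo". The futility rule stops it if the observed response difference, brexanolone minus control, is below 4%. The safety rule is meant to give a reasonably high chance of stopping when there is a true excess of deaths, and "a reasonably low probability of stopping the study when there is no such risk". No probabilities are attached. The section closes with "A detailed description of the interim analysis is included in the SAP".

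On how the rules are used, Protocol 7.4.1 says the DMC "will apply medical and statistical judgment during the performance of their activities", and Protocol 7.4.2 says "The DMC may also recommend stopping the study for futility at the time of interim analysis".

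On power, Protocol 13.8 says "The sample size of approximately 100 participants would provide 80% power" for 50% against 77% response. SAP 5.2 adds that this was computed "using Chi-square test with a two-sided Type I error rate (alpha) of 0.05". Neither mentions the stopping rules.

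SAP 6.1, 6.1.6 and 9.1.1.1 all say that the interim analysis will not be done. SAP 9.1.1.2 still has the DMC reviewing its results and still cites Protocol 13.8.1.1 for stopping criteria.

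**The concern.** With 25 per arm, a threshold just above 4 points is crossed by two excess deaths, which chance alone produces often. If about one trial in three with no mortality difference meets the rule, it is hard to square with the stated aim of a low false-stop probability. A reader cannot judge this from the text, because no figure is given and the SAP does not contain the promised detail.

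Two further points add to the doubt. A safety rule that fires this often could also end a trial of an effective drug, so an 80% power that ignores it could be too favourable. And adjacent SAP subsections disagree about whether an interim takes place. At stake would be an avoidable early stop, an overstated power figure, and uncertainty about which stopping criteria the DMC was working to.

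**Working it through.** **Inputs.** Interim size 25 per arm and both 4% thresholds: Protocol 13.8.1.1. Response 50% and 77%, total about 100: Protocol 13.8. Chi-square test, two-sided alpha 0.05: SAP 5.2. Mortality: no design value is given. The only indication is Protocol Section 5, which says that of COVID-19 patients in critical care "up to approximately 50% do not survive". Mortality values below are therefore assumptions.

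**1. The plan's own power.** With 50 per arm and pooled rate (0.50 + 0.77)/2 = 0.635:

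Power = Φ[(0.27·√50 − 1.96·√(2·0.635·0.365)) / √(0.50·0.50 + 0.77·0.23)] = Φ[(1.909 − 1.334)/0.6535] = Φ(0.879) = 81.0%.

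Exact enumeration of the same test gives 81.3%. The stated 80% reproduces as a fixed-sample figure.

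**2. Mortality rule, read literally.** One death is 1/25 = 4 points. More than 4 points means X_b − X_p ≥ 2, with X_b and X_p independent Binomial(25, p):

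| Equal true mortality | P(stop), 25/25 |
|---|---|
| 5% | 15.4% |
| 10% | 23.5% |
| 20% | 29.7% |
| 30% | 32.2% |
| 40% | 33.3% |
| 50% | 33.6% |

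With placebo mortality of 20-50%, a true excess of 10 points is detected 61-63% of the time, and one of 20 points 84-87%.

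These figures need exactly 25 per arm. A split of 24 and 26 breaks the 4-point steps, and the false-stop probability becomes about 35-41% at equal mortality of 20-50%. Protocol 13.8.1.1 also brings in available data from participants not yet at Day 28, so uneven denominators are likely.

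**3. Futility rule.** A difference below 4 points means brexanolone has no more responders than placebo. P(stop) is about 56% when response is equal (30-60%) and 2.9% at 50% against 77%. Two-stage enumeration (25 + 25 per arm) gives power of 80.9% with this rule binding, a loss of 81.3 − 80.9 = 0.4 point.

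**4. Both rules binding.** Stage 1 classes each participant as responder, dead or neither, and both rules are applied. The remaining 25 per arm are then added and the final chi-square test is done. Response is 50% against 77%, so brexanolone mortality cannot exceed 23%.

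| Placebo / brexanolone mortality | P(safety stop) | Power |
|---|---|---|
| 20% / 20% | 29.7% | 62.5% |
| 23% / 23% | 30.6% | 62.4% |
| 30% / 23% | 14.7% | 74.1% |
| 30% / 20% | 9.4% | 76.9% |
| 40% / 23% | 3.8% | 80.2% |
| 50% / 23% | 0.6% | 80.9% |

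At placebo mortality of 40-50%, closest to the only figure in the protocol, the loss is about 1 point or less. The fall to about 62% needs a 27-point response gain with no effect on mortality.

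**5. SAP wording.** Three places (6.1, 6.1.6, 9.1.1.1) cancel the interim explicitly, and two of them tie this to the early termination. The contrary text is confined to 9.1.1.2, a general description of DMC work that closely follows Protocol 13.8.1.2.

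**The case for a change.** The strongest case for a change is that it would cost only wording. One false stop in three sits badly with the stated aim. The SAP was to hold the detail and does not, and SAP 6.2 confirms there was no earlier approved SAP that might have held it. Protocol 13.8.1.1 calls its thresholds statistical rules for stopping, which reads as more than advice. The contradiction in SAP Section 9 needs no assumption at all, and it leaves open whether the 4% criteria still guided the DMC after the formal interim was dropped.

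Much of this stands as description. The false-stop probability is correct on its conditions, it is disclosed nowhere in these documents, and an uneven split makes it worse.

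What does not stand is the step to a fault in the plan. The protocol sets no numerical limit for a low probability, so the rule cannot be shown to miss it. At 25 per arm any mortality rule trades false stops against detection: requiring an excess of at least 16 points would cut detection of a true 10-point excess from 61-63% to 37-39%. A cautious rule in ventilated patients is a defensible choice. The text leaves open whether the rule binds, since the DMC weighs whether to stop and makes recommendations. Both documents place those recommendations under a DMC charter, which was not available here and may give the operating characteristics.

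**Conclusion.** No change is called for. No stated number is wrong: the 80% power reproduces and survives the futility rule with a loss of under 1 point. Quoting fixed-sample power alongside a safety rule is a normal reporting choice. A range of 62-81% would rest on mortality values that neither document supplies, and its lower end on an unlikely pairing of outcomes.

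The false-stop probability of about 30-34% assumes literal application, exactly 25 per arm and equal true mortality of 20-50%. It is about 35-41% with a 24/26 split. It is an undisclosed property of a deliberate trade-off, in an interim that was never to be run under the current SAP. The study ended because recruitment had become very difficult, not on DMC advice and not for safety, so disclosing the figure now would alter neither conduct nor conclusions.

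The missing SAP description follows from the cancellation. The sentences in SAP 9.1.1.2 are leftover wording, which a reader resolves from the three explicit cancellations. Whether the DMC kept the 4% criteria in view during its monthly reviews is a matter for its charter, and no final analysis depends on the answer.
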